4.1.2 Exclusion Criteria

Subjects who meet any of the following criteria are *not* eligible for the study:

1. Existence of other evidence that can explain pneumonia including but not limited to: Influenza A virus, influenza B virus, bacterial pneumonia (as suggested by the combined clinical picture, radiological findings and known laboratory results [eg, elevated procalcitonin >0.5 ng/mL and concomitant neutrophilia]), known fungal pneumonia, suspected fungal pneumonia based on compromised immune system with a history of past fungal infections, noninfectious causes, etc.
2. Known history of serious allergic reactions, including anaphylaxis, to IVIG or its preparation components.
3. Subjects with a history of thromboembolic event (TEE) within the last 12 months, such as deep vein thrombosis, pulmonary embolism, myocardial infarction, ischemic stroke, transient ischemic attack, peripheral artery disease (Fontaine IV).

4. Subjects with an underlying medical condition that can lead to hypercoagulable states and hyperviscosity such as antithrombin III deficiency, Factor V Leiden, Protein C deficiency, antiphospholipid syndrome, and malignancy.
5. Known history of selective IgA deficiency with antibodies against IgA.
6. Subjects with conditions such as human immunodeficiency virus (HIV) infection, known acute or chronic hepatitis B or C (HBsAg positive or HCV RNA PCR positive or currently treated with antivirals), pulmonary fibrosis, heparin induced thrombocytopenia (HIT), and moderate to severe renal dysfunction (per investigator discretion based on estimated glomerular filtration rate [eGFR] <59 mL/min/1.73 m², as defined by KDIGO Clinical Practice Guideline):
 - Moderately reduced GFR (G3a): GFR = 45 to 59 ml/min/1.73 m²
 - Moderately reduced GFR (G3b): GFR = 30 to 44 ml/min/1.73 m²
 - Severely reduced GFR (G4): GFR = 15 to 29 ml/min/1.73 m²
 - Kidney failure (G5): GFR <15 ml/min/1.73 m².
7. Currently requiring invasive mechanical ventilation or having received invasive mechanical ventilation in the last 30 days.
8. Known clinically significant preexisting lung, heart, neuromuscular or other disease that, in the investigator's opinion, would impact the subject's ability to complete study or may confound the study results.
9. Body weight > 125kg.
10. Women who are pregnant or breast-feeding.

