4.3 Withdrawal and Replacement of Subjects

4.3.1 Premature Subject Withdrawal

Subjects have the right to withdraw from the study at any time for any reason, without the need to justify their decision. The Investigator also has the right to withdraw subjects in case of AEs, poor compliance, or other reasons. Since an excessive rate of withdrawals can render the study non-interpretable, any unnecessary withdrawal of subjects should be avoided.

In addition to the ongoing safety monitoring and periodic Independent Data Monitoring Committee (IDMC) data review, the following rule will be implemented to apply temporary suspension of study drug administration, pending a safety investigation, for an unacceptable increased venous TEE or acute renal failure risk in the *Octagam 10%* group compared to the placebo group:

- For both venous TEEs or acute renal failures, the event risk will be calculated separately as (number of events reported)/(number of daily infusions) in both treatment groups, and the 90% confidence interval (CI) for the resulting risk ratio (R_{Octagam}/R_{Placebo}) will be determined by means of the / relrisk option of the SAS procedure FREQ. In case no events are observed in the placebo group, 1 will be added to each cell in the 2X2 table to enable this risk ratio evaluation. The stopping rule will be triggered if the lower confidence limit is greater than 1.0.
- This stopping rule will be applied whenever an unblinded evaluation is done, and a total of 40 daily infusions or more have been administered.
- For the first 40 daily infusions (ie, first 10 subjects that complete infusion cycle per protocol) a fixed rule will be applied by the IDMC to temporarily suspend study drug administration in case the number of related serious TEEs or acute renal failures as assessed by IDMC in the *Octagam 10%* group is triple the number in the placebo group. If no TEE or acute renal failure is observed in the

placebo group during this initial study phase, temporary suspension of study drug administration and safety investigation will be initiated if three related serious TEEs as assessed by IDMC or acute renal failures have been reported in the *Octagam 10%* group.

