For any withdrawals after study entry, the Investigator will obtain all the required details and document the reason(s) for discontinuation. If the reason for withdrawal of a subject is an AE, the main specific event or laboratory test will be recorded, and the Investigator will make thorough efforts to clearly document the outcome.

Other reasons for premature termination of subjects may be:

- Withdrawal of subject's consent.
- Pregnant and lactating subjects will be immediately excluded from the study.
- Investigator's opinion that the subject may be severely harmed if he/she continues study participation, namely by the treatment and procedures requested by the study protocol.
- Occurrence of a condition or disease that interferes with the study treatment or represents an exclusion criterion.
- Administration of IVIG other than *Octagam 10%*.
- Subjects do not comply with the study protocol.

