5.4 Dose and Dosing Schedule

Octagam 10% is available in glass bottles with different volumes of human immunoglobulin. Glass bottles of different volume should be combined in order to reach the required amount of IgG.

Octagam 10% or placebo will be administered by intravenous infusions on 4 consecutive days. The amount of *Octagam 10%* calculated on the dosage delivery schedule is 2 g/kg divided evenly over 4 days (0.5 g/kg/day).

If a subject is randomized to receive placebo, the same volume with the same infusion rate as would have been applied in case the subject would have been randomized to

2.0 g/kg *Octagam 10%* will be used. Therefore, they will receive an equal dose of placebo given over 4 days.

Body weight is to be measured at Screening or within 24 hours of first IMP administration and reported to the pharmacist or designee as it is needed for the preparation of the following study medication dosages.

All subjects should be clinically assessed for being adequately hydrated prior to IMP administration. TEE prophylaxis should be considered.

The initial infusion rate for each infusion episode will be:

- 0.01 mL/kg/min (60 mg/kg/h) for the first 30 minutes (\pm 5 minutes)
- if tolerated, advanced to 0.02 mL/kg/min (120 mg/kg/h) for the next 30 minutes (\pm 5 minutes)
- if tolerated, advanced to 0.04 mL/kg/min (240 mg/kg/h) for the remainder of the infusion

The interval of 30 minutes may be prolonged as per discretion of the investigator.

In subjects at risk for thromboembolic adverse reactions and acute renal failure (such as advanced age, hypertension, history of thrombotic episodes, subjects with prolonged periods of immobilization, concomitant nephrotoxic medication, diabetes mellitus, overweight, hypovolemia), *Octagam 10%* should be administered at the minimum rate of infusion practicable.

If AEs occur during the infusion, the rate is to be reduced to half the rate at which the event occurred, or the infusion is to be interrupted until symptoms subside. The infusion may then be resumed at a rate tolerated by the subject. In case of severe hypersensitivity or anaphylaxis, the infusion will not be restarted and all treatment with the IMP will be withdrawn. The subject will continue to be followed up in accordance with study-specific procedures as specified in the protocol with the exception that no further administrations of IMP will be performed. The subject will receive ongoing treatment in accordance with local SOC.

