6.1.2 Baseline/Infusion, Visits 1 to 4 (Day 1 to Day 4)

After screening and confirmation of eligibility, subjects will be randomized to receive either placebo or Octagam 10% (blinded). Administration of the first infusion must be started within 1 day (24 hours) after the screening visit. In this acute disease setting, the clinical status of patients can change rapidly. If a patient's eligibility status changes (eg, they require intubation and mechanical ventilation or meet other exclusion criteria) between initial confirmation of eligibility and randomization, they will not be randomized and will be considered a screening failure.

The first infusion of IMP should be initiated as soon as possible after randomization. Eligibility will not be re-assessed again between randomization and dosing. All randomized patients will therefore be dosed irrespective of changes in their clinical condition between randomization and dosing unless the Investigator decides that administration of the IMP would place the patient at additional risk.

The following activities/assessments will be performed **before** the IMP infusion on Day 1:

1. Confirmation of inclusion and exclusion criteria
2. Body weight (if not performed at Screening)
3. Vital signs
4. Physical Examination (if not performed at Screening or available from hospital admission notes, see Section 6.1.1)
5. Confirm medical history
6. Chest CT/Chest X-ray (at Day 1 if not available at Screening, see Section 7.3.6)
7. A-a Gradient (see Section 7.2.4)
8. Clinical Status and Oxygenation/Ventilator Status Evaluation
9. Blood sampling for clinical laboratory evaluations (specified in Section 7.3.4)
10. Randomization

The following activities/assessments will be performed **before** the IMP infusion on Days 2 through 4:

- Vital signs

- Clinical Status and Oxygenation/Ventilator Status Evaluation
- Blood sampling for clinical laboratory evaluations (specified in Section 7.3.4)

All blood sampling (Section 7.3.4) will be done **before** IMP infusion on all dosing days. If the Day 1 infusion commences within 8 hours of the blood collection for the Screening laboratory parameters, only those parameters not assessed at Screening need to be performed prior to the Day 1 infusion. Physical examination and body weight will be performed at Baseline (Day 1) only if it is not performed at Screening.

During and after IMP administration (Day 1 through Day 4):

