Cumulative duration in ICU will be imputed similarly, unless a patient has a useable discharge date (e.g. not occurring prior to prohibited medication use); in this case, the ICU discharge date will be set to the hospital discharge date. If a subject's last assessment identifies that IMV was used (and has no usable end date), the date on which it is no longer used will be assumed Day 33 unless the subject is discharged from the hospital prior to Day 33. If this occurs, the hospital discharge date will be used. IMV end dates will be imputed similarly, assuming that IMV ceases at the time of ICU discharge. Hospitalization, ICU, and IMV end dates for subjects who died prior to Day 33 during these events (e.g. after ICU admission or IMV initiation) will result in assumed end dates of Day 33 for endpoint analyses, so long as prohibited medication was not administered. Any dates on or after the start date of prohibited medication use will be considered unusable for imputation purposes; ongoing hospitalization, ICU, or IMV at the time of medication use will default to extrapolation to Day 33.

For the key secondary endpoint involving severe progression (ECMO, IMV, and death), subjects who withdrew early from study prior to Day 33 without evidence of events will be treated as not having the event. Sensitivity analyses will be conducted (1) treating them as failures (having the event at their last study visit) and (2) excluding them from the analyses. An additional analysis of these endpoints will be provided, treating prohibited medication use prior to Day 33 as an event, as well as allowing for status (event or success) without regard to prohibited medication use.

The outcomes for safety assessment and for additional efficacy analysis as well as exploratory endpoints will not be imputed if data is missing.

Please also refer to the more detailed descriptions in sections 12 to 18 of this SAP for additional details on the handling of missing data for particular endpoints and analyses.

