Cumulative duration on IMV through Day 33 and is defined as (IMV end date – IMV start date + 1). Subjects who do not require IMV will have a duration set to 0. Subjects who die on or prior to Day 33 or are still on IMV at Day 33, will have a duration set to their actual/projected Day 33 date for the IMV end date, so long as prohibited medication was not administered. If IMV end date is missing but subject is discharged from ICU or hospital, then IMV end date will be set to the earlier of the ICU or hospital discharge date. Otherwise, subjects without usable IMV end date information due to withdrawal or prohibited medication use will use a projected Day 33 date for the IMV end date. Comparisons between

treatment arms will be performed using a stratified Wilcoxon-Mann-Whitney (van Elteren) test with age category as a stratification factor.

Proportion of subjects with severe progression will be defined as the proportion that require ECMO, IMV or died prior to Day 33. For this analysis, subjects who use prohibited medication prior to the earliest of progression or Day 33 will not be included in analyses. Hypothesis testing for this endpoint will be conducted as described for the primary endpoint.

Length of time in ICU from randomization through Day 33 includes number of days spent in the ICU from randomization through Day 33 and is defined as [ICU discharge date – (later of ICU admittance date, randomization date) + 1]. Subjects who are not admitted to the ICU will have a duration set to 0. Subjects who die on or prior to Day 33 or are still in the ICU at Day 33, will have a duration set to their actual/projected Day 33 date for the discharge date, so long as prohibited medication was not administered. If ICU discharge date is missing but subject is discharged from hospital, then ICU discharge date will be set to hospital discharge date. Otherwise, subjects without usable ICU end date information due to withdrawal or prohibited medication use will use a projected Day 33 date for the ICU end date. Comparisons between treatment arms will be performed using a stratified Wilcoxon-Mann-Whitney (van Elteren) test with age category and baseline ICU status (In ICU at baseline versus not in ICU at baseline) as stratification factors.

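### Protocol 4.3.1 permits termination of a randomized subject who develops an exclusion criterion, such as ventilation or thrombosis, and no text then secures that subject's outcomes to Day 33

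*Protocol*

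**What the plan says.** Protocol 4.3.1 gives a general power: "The Investigator also has the right to withdraw subjects in case of AEs, poor compliance, or other reasons". Further grounds are introduced by "Other reasons for premature termination of subjects may be", and one of them is "Occurrence of a condition or disease that interferes with the study treatment or represents an exclusion criterion". The same section asks that unnecessary withdrawal be avoided. Under 4.3.3, withdrawn subjects are not replaced.

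Protocol 4.1.2 excludes subjects "Currently requiring invasive mechanical ventilation or having received invasive mechanical ventilation in the last 30 days" (criterion 7), those with a thromboembolic event in the past 12 months (criterion 3), and those with moderate to severe renal dysfunction, judged by the investigator from eGFR (criterion 6).

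IMV is also category 5 of the primary scale (3.1.1), a component of severe progression, and the basis of the IMV-duration endpoint (3.1.2.1). Section 1 names thromboembolic events and acute renal failure as side effects of IVIG, and the suspension rule in 4.3.1 monitors venous thromboembolic events and acute renal failure.

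For severe progression, SAP 4.1 (like Protocol 9.2.5) says that "subjects who withdrew early from study prior to Day 33 without evidence of events will be treated as not having the event". For IMV duration, SAP 14 says: "Otherwise, subjects without usable IMV end date information due to withdrawal or prohibited medication use will use a projected Day 33 date" as the end date.

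**The concern.** Exclusion criteria define who may enter. Applied after randomization, they become a list of things that happen to patients with severe COVID-19, some of them because of the treatment. If a site ends participation when one of these occurs, data are lost for reasons tied to prognosis and possibly to arm. That kind of missingness cannot be repaired in the analysis. At stake are the Day 7 and Day 14 status endpoints, severe progression, IMV and ICU duration, time to discharge and Day 33 mortality.

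**Working it through.** **1. The plan's own allowance for loss.** Protocol 9.1 inflates 88 per arm for 15% drop-out: 88/0.85 = 103.5, rounded up to 104 per arm, 208 in all. This reproduces. Power for 0.60 versus 0.80, two-sided 0.05, is Φ{[0.20 − 1.96·√(2·0.7·0.3/n)] / √[(0.24 + 0.16)/n]}. At n = 88 this is 83.1%, so the claim of at least 80% holds. If lost subjects were simply non-evaluable (not the plan's rule), loss from 104 per arm would give:

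| Loss | Evaluable per arm | Power |
|---|---|---|
| 20% | 83 | 80.9% |
| 25% | 78 | 78.4% |
| 30% | 72 | 75.0% |

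Power is therefore not the main issue. How a terminated subject is scored is.

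**2. Does the clause reach outcome events?** Yes. New IMV matches criterion 7, a new thromboembolic event matches criterion 3, and new renal dysfunction can match criterion 6. Protocol 6.1.2 itself treats intubation before randomization as meeting an exclusion criterion.

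**3. Does termination mean leaving the study?** Most of the text points that way. The heading of 4.3.1 concerns subject withdrawal, and 4.3.3 and 4.6 speak of withdrawal from the study. Table 2 in 6.1.8 sets early termination against completing the core trial, and SAP 9 does the same in the disposition table. Against this, 7.3.2.1 defines withdrawal for an adverse event as stopping study drug. The protocol does not settle it.

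**4. Does any text keep such a subject in follow-up?**

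| Place (Protocol) | Trigger | Follow-up |
|---|---|---|
| 4.2 | Prohibited medication | Infusions stop, follow-up continues |
| 5.4 | Severe hypersensitivity or anaphylaxis | "The subject will continue to be followed up in accordance with study-specific procedures as specified in the protocol" |
| 7.3.2.7 | Anaphylaxis | Subject withdrawn from the study |
| 5.4, events that prevent dosing | Thrombotic event, acute kidney injury | Not stated |
| 6.1.7 | Withdrawal for an adverse event | Until the event resolves |
| 4.3.1 | Condition matching an exclusion criterion | Not stated |

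No row secures Day 33 for the last case. On anaphylaxis, 5.4 and 7.3.2.7 conflict directly.

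**5. Two illustrative subjects (days and categories assumed; events after termination assumed not to reach the database).**

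*Subject A:* baseline category 3; category 3 before infusion on Day 2; thrombosis on Day 2; terminated Day 3, not in ICU; IMV from Day 6; death on Day 12.
- Day 7: true category 5, carried forward as 3, scored a success.
- Day 14: true category 6, carried forward as 3, scored a success.
- Severe progression: true event, scored as none.
- IMV duration: scored 0, because none is recorded. With full data the rule for deaths would give 33 − 6 + 1 = 28.

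*Subject B:* baseline category 3; IMV in ICU from Day 3; terminated on IMV; extubated Day 10; category 3 on Day 14; discharged Day 20.
- Day 7: imputed 5, a failure, which agrees with the truth.
- Severe progression: counted correctly.
- Day 14: true success, imputed 5, scored a failure.
- IMV duration: true 10 − 3 + 1 = 8. With no known end or discharge date, 33 − 3 + 1 = 31. If the Day 20 discharge date is known, 20 − 3 + 1 = 18.
- Time to discharge: true event at Day 20, censored at Day 33 if the date is missing.

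The errors for A favor the subject's arm and those for B go against it, so there is no single direction.

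**6. Deaths after termination.** Protocol 7.3.7 asks for reports of deaths within 4 weeks of the last administration, but requires no proactive monitoring for post-study serious events. A last dose on Day 4 gives 4 + 28 = Day 32; a last dose on Day 2 gives Day 30. Both fall short of Day 33. The mortality definition in SAP 14 states no rule for early withdrawal.

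**The case against.** The strongest reply is that this is permissive boilerplate in a protocol that plainly expects to follow ventilated patients. Unnecessary withdrawal is discouraged. Protocol 7.2.2 records ventilation at and between visits, and the duration rules provide for subjects still on IMV at Day 33. On the 7.3.2.1 definition, termination could mean stopping drug only. All of this makes frequent use of the clause unlikely, but none of it forbids that use or says what follow-up is owed.

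The safeguards are also real. Known death, ECMO, IMV or ICU admission overrides the carried-forward value (Protocol 9.2.5, SAP 4.1). SAP 13 plans worst-case and complete-case analyses of the primary endpoint, and SAP 4.1 plans analyses of severe progression with withdrawals as failures and excluded. Adverse events are followed to resolution or stability (7.3.2.7), and registry contact continues after early termination (Table 2), although SAP 1 puts registry analysis out of scope. These limit the loss without recovering the missing outcomes.

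Four stronger readings are tempting and not supported:
- *Sites must terminate intubated subjects.* The list says only what reasons may be.
- *Deaths after termination need not be recorded.* Protocol 7.3.2.6 and 7.3.7 call for reporting within 4 weeks of treatment. The gap is passive capture and the last days before Day 33.
- *Thrombotic or renal toxicity drops out of the safety record.* The triggering event has already occurred and is reported; 4.3.1 requires its outcome to be documented. Only later deterioration is exposed.
- *Section 6.1.2 contradicts the clause outright.* "All randomized patients will therefore be dosed irrespective of changes in their clinical condition between randomization and dosing" covers only the interval before the first infusion, with an exception for investigator judgment. It does not address later events or retention.

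**Conclusion.** The concern holds as a gap in the text. The protocol allows termination for events that are themselves outcomes or known drug risks, and nothing keeps those subjects under observation to Day 33. The larger exposure is the thrombotic or renal case terminated before deterioration, which can score as stable and progression-free in the main analysis. For IMV cases the event is already counted; what may be lost is later death, true duration and discharge.

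No count of affected subjects or missed deaths can be drawn from the documents. It would need assumed rates of IMV, later mortality, termination and tracing. The pilot's ventilation figures in Protocol 1.1 (7/12 versus 2/14) come from a subset with A-a gradient above 200 mmHg and do not supply them. The conclusion assumes that at least some sites read termination as study exit and that later information does not reach the database. The disposition table in SAP 9 will show terminations and primary reasons by arm.

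**What to change.** In Protocol 4.3.1, treat stopping study drug and ending study follow-up as two separate decisions. State that onset after randomization of a condition matching an exclusion criterion, or an investigator's decision to stop study drug for an adverse event, does not by itself end follow-up. Such a subject keeps the Day 7, 14, 21 and 33 assessments, at minimum vital, ventilation, ICU and discharge status, unless consent to data collection is withdrawn.

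Leave every rule on stopping study drug unchanged. Deleting the exclusion-criterion phrase alone would not be enough. The general power to withdraw and the ground of interference with study treatment would remain, and the deletion could be read as removing a reason to stop treatment.

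Reconcile 4.2, 4.3.1, 5.4, 6.1.7, 7.3.2.1 and 7.3.2.7 on this point, including the conflict between 5.4 and 7.3.2.7 over follow-up after anaphylaxis.

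Cost: a short amendment and a few more follow-up contacts.
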